#### *C. Statistical Analysis Plan*

Results will be synthesized across the data sources and implementation outcomes, and utilized to assess the reach and effectiveness of social influence campaign strategies. Findings from the review of programme logs, social media metrics, and cross-sectional surveys will be reported. Costing data and ranges of intervention fidelity and penetration parameters will be used to inform programme activities. A comparison of the social influence campaign intervention vs standard of care at achieving PrEP uptake (primary), 1-month PrEP persistence (secondary) and 4-month PrEP persistence (secondary) will be key outcomes. Cluster level proportions of clients within the TB HIV Care PrEP programme who initiate PrEP will be compared between the main study arms using the unpaired t-test after a log-transformation if necessary. A secondary analysis will adjust for residual confounding by age and other individual characteristics through a two-stage logistic regression residuals approach. A similar approach will be used for the secondary outcomes and the comparison between sub-arms within the intervention main arm. Changes in PrEP knowledge, attitudes and social support across intervention and control areas over the two time periods (pre- and post-intervention) will be estimated using a difference in differences approach. Prevalence of PrEP knowledge, attitudes and social support across intervention and control areas over the two time periods (pre- and post-intervention) will be summarized by questions/item. Multivariate analysis will be conducted to generate patterns of responses by theme (e.g. perceptions of PrEP). Changes over time will be analysed using the difference in differences approach that uses suitable regression models (e.g. logistic, linear) to study the effect of time period and study arm, as well as their interaction, on the responses.

Analysis of data will be conducted using STATA Version 15.0.

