### *A. Randomization*

The 10 districts /sites in which THC provides PrEP will be taken as unit of randomization for the first layer of comparison. Five of the sites will be randomized to the standard of care PrEP promotion arm, and five to the PrEP promotion+enhanced social media campaign arm. Constrained covariate randomization will be applied taking into account the baseline number of annual PrEP initiations, the number of subdistricts within a site, the number of rural subdistricts, mean district HIV prevalence, and program type (AGYW or FSW or a combination of the two).

Within the PrEP promotion+enhanced social media campaign arm, wards will be randomized to 4 sub-arms receiving different combinations of the enhancements described in Table 1. The

randomization will be stratified by site and effort will be made to reduce potential contamination between wards.

All randomization activities will be completed by the team biostatistician who specializes in cluster randomized trials, [name] [name] (Co-Investigator).

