#### *B. Sample Size Considerations*

**Social influence campaign (CRT):** The primary outcome for this study will be PrEP uptake within the TB HIV Care programme. Each of the 10 cities in which TB HIV Care provides PrEP will be included as clusters. Assuming between 500 and 1000 PrEP-eligible women reached by the TB HIV Care PrEP programme per geographic region annually, we considered a coefficient of variation (CV) ranging from 0.25 to 0.4, and a minimum improvement in uptake of 10 percentage points (5% to 15%). With a conservative CV of 0.4, 5 clusters per arm will provide 87% power to detect this difference at an  $\alpha=0.05$  level of significance. For the second layer of randomization for enhanced social influence activities, a total of 216 wards (a smaller unit of subdivision used in South Africa to divide regions for political and administrative purposes) exist across the 5 intervention sites, which will be randomized across four sub-arms. There will be roughly 54 wards per sub-arm each with at least 10 PrEP-eligible women. Overall, arm 2 is hypothesized to have PrEP initiations of 15% where the least effective sub-arm [no additional enhancement] has an uptake rate of ~10% and the most effective sub-arm [2d which combines PrEP champions and PrEP community mobilization will have] will have an uptake rate of up to ~20%. Having at least 30 venues per sub-arm would provide 84% power, at a 5% level of significance, assuming a conservatively high CV of 0.4, to detect this difference. As this will be an exploratory investigation, the emphasis will be on the additional yield by the enhancements and thus no correction for the multi-arm hypothesis testing will be conducted.

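### Wards are randomised within site, but the sub-arm comparison does not name site; adding site as a fixed effect gains a little precision at almost no cost

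*Combined protocol and SAP*

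**What the plan says.** Section 7.A sets out two layers of randomisation. For the first: "The 10 districts /sites in which THC provides PrEP will be taken as unit of randomization for the first layer of comparison". For the second, wards in the intervention arm go to four sub-arms, and the "randomization will be stratified by site and effort will be made to reduce potential contamination between wards". The footnote to Table 1 in section 4 gives about 216 wards and describes each as being randomised.

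Section 7.C states that cluster-level uptake proportions "will be compared between the main study arms using the unpaired t-test after a log-transformation if necessary". One adjusted analysis follows: "A secondary analysis will adjust for residual confounding by age and other individual characteristics", by a two-stage residuals method. The sub-arms get a single sentence: "A similar approach will be used for the secondary outcomes and the comparison between sub-arms within the intervention main arm". Site is not named in any sub-arm analysis.

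For the district calculation, section 7.B says "we considered a coefficient of variation (CV) ranging from 0.25 to 0.4". It uses 0.4 for the sub-arm calculation, calls that layer exploratory, and puts the weight on how much extra the enhancements yield.

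**The concern.** When wards are allocated within site, each sub-arm gets a near-equal share of every site. Differences in uptake between sites therefore largely cancel from the sub-arm contrast. An unpaired t-test on all wards does not know this: it counts the site differences as ward-to-ward noise. Its standard error is then larger than the design warrants, its intervals are too wide, and its true size falls below the nominal 5%.

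What is at stake is precision in the layer meant to show which enhancement adds what. The largest planned contrast hardly suffers. The smaller ones do: one enhancement against none, or both against one.

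**Working it through.** **1. The plan's own figures.** With c clusters per arm, m women per cluster and between-cluster CV k, power = Φ(√[(c−1)(p1−p0)²/v] − 1.96), where v = p0(1−p0)/m + p1(1−p1)/m + k²(p0²+p1²).

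- Districts (c = 5, 5% against 15%, k = 0.4): at m = 1000, v = 0.000175 + 0.004 = 0.004175, √(0.04/0.004175) = 3.095, power 87.2%. At m = 500 it is 85.8%. Stated: 87%.
- Sub-arms (c = 30, m = 10, 10% against 20%, k = 0.4): v = 0.009 + 0.016 + 0.16 × 0.05 = 0.033, √(0.29/0.033) = 2.964, power 84.2%. Stated: 84%. With c = 54, √(0.53/0.033) = 4.007, power 98.0%.

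Both stated figures reproduce.

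**2. Inputs for the comparison with and without site.** From section 7.B: about 54 wards per sub-arm, at least 10 women per ward, ward CV 0.4, and 500 to 1000 women per district per year. Over five districts and 216 wards that gives 500 × 5/216 = 11.6 to 1000 × 5/216 = 23.1 women per ward, hence 12 to 23. Assumed: the site CV (0.15, or the plan's district range 0.25 to 0.4), and 15% as an intermediate sub-arm rate. Section 7.B does not say whether the ward CV of 0.4 is total or within site, so both readings are shown.

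**3. Simulation.** Five sites, lognormal site and ward effects, binomial counts, raw proportions, allocation balanced within site; 54 wards per sub-arm. The interval ratio is the average width with site divided by the average width without.

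| Site CV; reading of ward CV 0.4 | Interval ratio, 10% v 20% (10 women) | Interval ratio, 10% v 15% (12–23 women) | Power, 10% v 15%, t-test → with site |
|---|---|---|---|
| 0.15; total | about 0.99 | 0.984 | 78.9 → 79.9 |
| 0.25; total | 0.965 | 0.955 | 80.0 → 82.5 |
| 0.25; within site | 0.968 | 0.960 | 75.4 → 77.8 |
| 0.4; within site | 0.927 | 0.912 | 70.4 → 76.4 |

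Taking the ratio trial by trial and then averaging gives slightly smaller gains: 3 to 4% at site CV 0.25, and 7 to 8% at site CV 0.4. For 10% against 20% with 54 wards, power rises by 0.2 to 0.7 points. With only 30 wards (within-site reading) it goes from 84.5 to 85.7 at site CV 0.25 and from 80.7 to 84.4 at 0.4.

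**4. Size.** If site holds half the between-ward variance, the nominal 5% t-test rejects a true null about 4.4% of the time at 10% uptake with 10 women, and about 3% at 20% uptake with 23 women. With site in the model the figure is 4.8 to 5.2%.

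**5. Cost if sites do not differ.** Four degrees of freedom: 106 falls to 102 with 54 wards (critical t 1.983 to 1.984), and 58 to 54 with 30 wards (2.002 to 2.005). The largest power loss seen was 79.2 to 78.8, or 0.4 points.

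**6. Form of the model.** One four-arm model with a single pooled variance is unsafe, because the variance of a proportion rises with uptake: pairwise size ran from 1.6% to 8.6%. Fitting each pair of sub-arms separately gave 4.5 to 5.3%; the four-arm model with HC2 standard errors gave 4.6 to 5.3%.

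**7. Scale.** At 10% uptake and 10 women, a ward has no initiations with probability 0.9^10 = 0.35, before any ward-to-ward variation. A log scale would need a rule for about a third of such wards.

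**The case against.** **Little is at stake.** The test is valid, it errs on the safe side, the layer is exploratory, and the planned contrast is already about 98% powered with 54 wards. All of this stands. It makes the point an inexpensive improvement, not the correction of an error.

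**The omission is inferred.** No sentence excludes site. The sub-arm sentence says only that the approach will be similar, and it follows directly after a regression-based method. This stands too. If the sponsor already means to include site, one sentence settles the matter.

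**Site differences are not established.** A reader might infer that the plan expects sites to differ with a CV of up to 0.4. The documents do not support that: section 7.B labels 0.4 a conservative planning value, and section 2 describes the challenges in uptake as similar across sites, although that does not say uptake rates are equal. A reader might also take 0.4 as both the site CV and the total ward CV, which gives intervals 10 to 12% shorter. That is a limiting case in which wards within a site do not differ at all, and I do not rely on it.

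**The ward inputs are soft.** The 84% is stated for 30 venues, read here as wards. The 12 to 23 women come from annual reach, whereas champions and mobilisation run for 6 months; a shorter window means fewer women per ward and smaller gains. The 15% rate is the plan's figure for the whole intervention arm. These points stand as limits on the size.

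**The district layer.** A reader might infer that the same argument calls for adjusting the primary comparison for the factors used there: "Constrained covariate randomization will be applied taking into account the baseline number of annual PrEP initiations", among others. The documents do not show that any of these predicts uptake; the baseline factor is a count, while the outcome is a proportion. With ten districts, adjustment costs power if the factor is not prognostic: for 5% against 15%, simulated power falls from 92.3% to 88.7% for baseline initiations.

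**Conclusion.** The point holds as an efficiency gain in the sub-arm comparison. The planned test is not anti-conservative, and neither the primary analysis nor the stated powers are in question. The size depends on a quantity the documents do not give, the site share of ward variance. At a site CV of 0.15 to 0.25 the gain is modest. It becomes material for the smaller contrasts only if sites differ about as much as wards do within a site. It is near zero for 10% against 20% with 54 wards, and very slightly negative if sites do not differ. The figures assume that wards are randomised singly within site, as the Table 1 footnote suggests, and that sub-arms are close to balanced in each site. If balance is lost, for example through the effort to limit contamination, including site also removes the site imbalance from the contrast.

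**What to change.** In section 7.C, replace the sub-arm unpaired t-test with a ward-level linear regression of uptake proportion on sub-arm, with site as a fixed effect. Fit it to each pair of sub-arms, or use heteroscedasticity-robust standard errors in a four-arm model. Use the untransformed scale, so that wards with no initiations stay in and the effect reads in percentage points.

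State that wards are randomised singly within site. If neighbouring wards are allocated together to limit contamination, make that group the unit of analysis.

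Leave the district-level primary t-test as it is; no adjusted district-level analysis is requested.

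The cost is SAP wording and four degrees of freedom; site is already recorded for the stratification. The one thing given up is the optional log-transformation for this exploratory layer.

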#### **4. STUDY DESIGN:**

This grant combines evaluation of ongoing PrEP programme implementation (previous work) with modified, programme informed implementation strategies for testing through two short-duration cluster randomized trials (CRTs). Specifically, this study protocol is focused on PrEP programme optimization through modifying the implementation strategies of ongoing programmatic activities by adjusting the delivery modalities and actors promoting PrEP within the community. The effect of these modifications on PrEP uptake (primary outcome) and continuation (secondary outcome) will be tested using an initial CRT. A second CRT focused primarily on PrEP continuation (retention) will be included in a separate, future protocol.

TB HIV Care is a South African non-profit organization that works directly with the Department of Health as the country's largest PrEP provider for AGYW and FSW. TB HIV Care has initiated over 33,000 women at high risk for HIV infection on PrEP, and has 13 active sites as of 2021. Of note, these are two PrEP programmes that are run by TB HIV Care (8 of the 13 active sites are part of the FSW programme and 5 of the 13 active sites are part of the AGYW programme). **The proposed study design leverages a cluster randomized trial design as some intervention components may not be feasibly randomized at the individual-level (e.g. PrEP peer ambassadors operating within venues/community locations, community mobilization and social media ads).** This trial is feasible given the short duration of the outcomes measured (PrEP uptake and 1- and 4-month PrEP persistence) and utilization of routine programme data for primary outcome ascertainment, and the testing is an adaptation of existing interventions. Based on the programme team's experience and PrEP barriers literature, this first CRT will focus on generating sustained PrEP demand, but also destigmatizing PrEP within young women's social environments (e.g. family, friends, partners). **CRT1 is described within this application.** The second CRT will likely optimize peer support mechanisms during the early days of PrEP use, but this will be refined in late 2022 based on the programme's input and a separate protocol will be submitted surrounding CRT2.

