## **5. STUDY POPULATION:**

The study population includes female sex workers (FSW) and adolescent girls and young women (AGYW) who will participate in the TB HIV Care programme over a one year period (12-months) across multiple sites starting at the launch of the campaign. Overall, since programme inception, TB

HIV Care has implemented PrEP services for women in 17 sites across 6 provinces. Currently 13 sites are actively implementing PrEP programming in 10 districts across 4 provinces and will contribute to the CRT aggregate level data: OR Tambo, Eastern Cape (AGYW & FSW); Zululand, KZN (AGYW); uThukela, KZN (AGYW); uMgungundlovu, KZN (AGYW & FSW); eThekwi, KZN (AGYW & FSW); Ehlazeni, Mpumalanga (FSW); Gert Sibande, Mpumalanga (FSW); Nkangala, Mpumalanga (FSW), [name], North West Province (FSW); and Ngaka Modiri Molema, North West Province (FSW). Here, participation is defined as receiving  $\geq 1$  of the following HIV prevention services offered to FSW and AGYW by TB HIV Care: STI screening and/or treatment, pregnancy testing, HIV testing, or any other service that would result in having a health screening form on file. All clients seen by TB HIV Care are assigned to HIV acquisition risk groups (FSW, AGYW, or others) the first time they are seen based on risks reported on a standardized intake form. Women screening positive for HIV on their first encounter with the programme during the study period will be excluded.

The time period of interest will be 12-months. We anticipate the social media campaign to launch in February 2022, in which case the study period would be February 1, 2022-January 31, 2023. The one year of follow-up will begin at the time of campaign launch.

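### The district randomisation is constrained on programme type but the primary t-test ignores it: if FSW and AGYW uptake differ by more than about a quarter, the test is conservative and forgoes power

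*Combined protocol and SAP*

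**What the plan says.** **Design.** Section 7.A says: "Constrained covariate randomization will be applied taking into account the baseline number of annual PrEP initiations". The other constraining covariates are the number of subdistricts, the number of rural subdistricts, "mean district HIV prevalence, and program type (AGYW or FSW or a combination of the two"). The split is 1:1: "Five of the sites will be randomized to the standard of care PrEP promotion arm" and the other five to the campaign. No rule states how tight the constraint is.

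**Analysis.** Section 7.C says the district proportions "will be compared between the main study arms using the unpaired t-test after a log-transformation if necessary". No constraining covariate enters this comparison, and no test restricted to the allowed allocations is mentioned. The only adjustment comes later: "A secondary analysis will adjust for residual confounding by age and other individual characteristics", by a two-stage logistic residuals method. Programme type is not named there.

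**Data available.** Section 5 lists each district's programme(s) and says: "All clients seen by TB HIV Care are assigned to HIV acquisition risk groups (FSW, AGYW, or others) the first time they are seen". Programme type is therefore known for every district before launch.

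**The concern.** Balancing a covariate that predicts the outcome removes it from the true sampling error of the arm difference. An unadjusted t-test does not know this. It estimates its standard error from the spread within arms, and FSW-only and AGYW-only districts still sit side by side within each arm. If uptake differs by programme, the standard error is too large for the design used. The test then rejects a true null less than 5% of the time, the matching interval is wider than it should be, and precision gained at randomisation is lost at analysis.

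With ten clusters, precision is scarce. If the campaign achieves less than the planned tripling of uptake, or nothing at all, the width of the interval decides what the trial can say.

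**Working it through.** **1. Inputs from the documents.** Five districts per arm; 5% versus 15% uptake; 500 to 1000 women per district; CV 0.4; alpha 0.05; stated power 87% (Section 7.B). The Section 5 list gives 5 FSW-only, 2 AGYW-only and 3 mixed districts. This agrees with Section 4: "8 of the 13 active sites are part of the FSW programme and 5 of the 13 active sites are part of the AGYW programme" (5 + 3 = 8 and 2 + 3 = 5).

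**2. The plan's own figure.** For an unmatched cluster trial, power = Φ(√[(c−1)(p1−p0)² / V] − 1.96), where V = p0(1−p0)/m + p1(1−p1)/m + k²(p0²+p1²). With c = 5, k = 0.4 and m = 750, V = 0.00423, the root is 3.07 and power is 86.7%. It is 85.8% at m = 500 and 87.2% at m = 1000. The stated 87% reproduces, two-sided.

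**3. Balanced allocations.** Of C(10,5) = 252 splits, 120 balance programme type as closely as possible: FSW-only 3/2, AGYW-only 1/1, mixed 1/2, and the mirror image (60 + 60). Exact balance of this kind is an assumption.

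**4. Mechanism, checked by hand.** Score districts 0 (FSW only), 0.5 (both), 1 (AGYW only). The overall variance of the score is 0.1525. In a balanced split the arm means are 1.5/5 = 0.3 and 2/5 = 0.4, a difference of only 0.1. The pooled within-arm variance is (1.525 − 0.025)/8 = 0.1875. Suppose programme type explains a share R² = 0.30 of between-district variance (total set to 1):
- Variance the t-test estimates: 0.4 × (0.70 + 0.30 × 0.1875/0.1525) = 0.428.
- True mean squared error of the difference: 0.4 × 0.70 + 0.30 × 0.01/0.1525 = 0.300.
- Ratio of standard errors: √(0.428/0.300) = 1.19. The effective critical value is 2.306 × 1.19 = 2.75, which on 8 df is a two-sided level of about 2.5%. Simulation gives 2.4%.

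**5. Normal-model simulation at the planned effect (2.19 SD).** R² is an assumed range.

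| R² | Type I error, t-test | Power, t-test (8 df) | Power, AGYW score (7 df) | Power, three-level factor (6 df) |
|---|---|---|---|---|
| 0 | 5.0% | 85.5% | 83.5% | 80.0% |
| 0.05 | 4.6% | 85.8% | 85.6% | 82.0% |
| 0.10 | 4.0% | 85.9% | 87.1% | 83.8% |
| 0.30 | 2.4% | 86.7% | 93.7% | 91.5% |
| 0.50 | 0.8% | 88.0% | 98.4% | 97.5% |

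Break-even is near R² = 0.05 with one adjustment df and near 0.15 with two. Coverage of the unadjusted 95% interval is 97.6% at R² = 0.30 and 99.2% at 0.50. Without the constraint, type I error stays near 5%.

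**6. Simulation on the uptake scale.** Gamma district effects with total CV 0.4, binomial counts with 500 to 1000 women, mean control uptake 5%, mixed districts midway. The AGYW:FSW ratio is assumed. It converts to R² as follows:
- Ratio 2: relative rates 1, 1.5 and 2 have mean 1.35 and variance 0.1525. R² = (0.1525/1.35²)/0.4² = 0.52 (uptake 3.7% and 7.4%).
- Ratio 1.5: mean 1.175, variance 0.0381, R² = 0.17.
- Ratio 1.25: mean 1.0875, variance 0.0095, R² = 0.05, the break-even point (uptake 4.6% and 5.7%, a gap of about 1 point).

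| Ratio | Type I error, t-test | Type I error, adjusted | Interval with adjustment | Power 5% vs 10%, t-test → adjusted |
|---|---|---|---|---|
| 1 | about 5% | about 5% | 3% wider | 57% → 55% |
| 1.2 | 4.5% | about 5% | about equal | 57.0% → 56.3% |
| 1.5 | 3.5% | 5.0% | 7-8% narrower | about 57% → 63% |
| 2 | about 1% | about 5% | 29% narrower | about 53% → 83% |

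At 5% versus 15%, the unadjusted test keeps 90-92% power at every ratio. A log-transformation does not remove the problem: at ratio 2 type I error is 1.3%, and power for a doubling is 61% against 85% with adjustment. The type I error and interval-width figures are for no arm difference. With a large arm effect on the raw scale, unequal variances lower the coverage of both analyses, so the over-coverage should not be carried over to a tripling.

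**The case against.** Several points on the other side stand.

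- **Small gaps.** A reader might infer that power is lost whenever the two programmes differ. That is not so. Below a ratio of about 1.25, the df spent costs more than the adjustment returns.
- **Power for a doubling.** A reader might infer that this omission is why an effect smaller than a tripling could be missed. Unadjusted power for 5% versus 10% is about 57% even when the programmes do not differ. That comes mainly from having ten clusters at CV 0.4.
- **Size of the gap.** The documents give no FSW or AGYW uptake. Section 2 describes overlapping programmes and similar uptake challenges across sites, which gives no support to a twofold gap.
- **Tightness of the constraint.** Section 7.A lists programme type last of five covariates and sets no balance rule. A looser constraint would shrink the effect; with no constraint, type I error is close to 5%.
- **Direction.** The error is conservative. There is no bias and no excess of false positives.
- **No interval is specified.** Section 7.C names a test only. The statements about width and coverage concern the interval that goes with that test.

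One point stands only in part. Risk group could be read into the individual characteristics of the secondary analysis, but that leaves the primary test unchanged.

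**Conclusion.** The mismatch between Sections 7.A and 7.C is real, and its direction is clear: the primary test is conservative and forgoes power if programme type is balanced and uptake differs by more than about a quarter. At an assumed ratio of 1.5 the cost is modest (type I error about 3.5%; about 6 points of power for a doubling). At ratio 2 it is large (about 1%; about 30 points), but that requires programme type to explain about 52% of between-district variance, which nothing in the documents establishes.

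This does not show that the sample size is wrong. The 87% reproduces, and the unadjusted test retains it. What is at issue is precision that the design may already have paid for. The figures rest on near-exact balance of programme type, a total CV of 0.4, and mixed districts lying midway between the others. It is a cheap improvement worth making, not a flaw that invalidates the analysis.

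**What to change.** In Section 7.C, make the primary district comparison a cluster-level regression of the district proportion (or its log) on arm plus one covariate fixed before launch: programme type, scored by the pre-campaign AGYW share, or 0, 0.5 and 1 for FSW only, both and AGYW only. Use t with 7 df. Keep the plain t-test as a sensitivity analysis. State that the other constraining covariates do not enter, because adjusting for all five with ten districts would leave very few df.

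Do not use the AGYW share of women offered PrEP during the trial. It is counted over the 12 months after launch, and a demand-generating campaign could change it.

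A permutation test restricted to the allowed allocations, with the same baseline covariate, is an acceptable alternative. The allowed set must then be kept large enough: with mirror-image allocations the smallest two-sided p-value is 2/N, so at least 2/0.05 = 40 allocations are needed.

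Cost: a sentence or two in the plan and no new data. If the programmes do not differ, one df is lost (critical value 2.306 to 2.365, a ratio of 1.03), so the interval is about 3% wider and power falls by 2-3 points. The choice should be fixed before the outcome data are seen, since an adjustment picked after looking at ten values would not be credible.

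### The optional log-transformed t-test cannot be computed on all wards in the exploratory sub-arm comparisons, because wards with no initiations will be common and the plan has no rule for them

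*Combined protocol and SAP*

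**What the plan says.** Section 7.C (Statistical Analysis Plan) compares cluster-level proportions initiating PrEP between the main arms "using the unpaired t-test after a log-transformation if necessary". Soon after, it adds: "A similar approach will be used for the secondary outcomes and the comparison between sub-arms within the intervention main arm".

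The clusters change between these two uses. The main arms are 10 districts. In the second layer, according to section 7.A, "wards will be randomized to 4 sub-arms receiving different combinations of the enhancements described in Table 1", with randomization stratified by site. Section 7.B describes these clusters: "There will be roughly 54 wards per sub-arm each with at least 10 PrEP-eligible women". It assumes uptake of about 10% in the least effective sub-arm (2a) and up to about 20% in the most effective (2d). On power it says "Having at least 30 venues per sub-arm would provide 84% power", with a CV of 0.4 and a 5% significance level. It calls this layer exploratory, with the emphasis on the extra yield from the enhancements.

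The plan gives no criterion for when a transformation is needed, no rule for a cluster with zero initiations, and no rule for a ward that has no initiators when persistence is analysed.

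**The concern.** A log-transformed t-test suits district proportions built on hundreds of women. A ward may contribute only 10 women, of whom one or two are expected to initiate. Many wards will then have a proportion of exactly zero, and the log does not exist. An analyst who takes up the log option must drop those wards or alter their values, and the plan guides neither choice.

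Dropping them would not be neutral. Zero wards are more frequent where uptake is lower, so the weaker sub-arm would lose more of its poor results and the contrast would move toward the null. The size of the contrast is what section 7.B wants to learn from this layer. Because the scale and the handling of zeros are both open, they could also be settled after the data are seen.

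Persistence has a separate difficulty. Its denominator is initiators, so a ward with none has no proportion, transformed or not. A ward with one or two initiators would count as much in an unweighted t-test as a ward with many.

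**Working it through.** **Inputs from section 7.B.** Uptake p0 = 0.10 (2a) and p1 = 0.20 (2d); CV k = 0.4; at least m = 10 women per ward; about 54 wards per sub-arm (216 / 4), with 30 clusters in the power statement; 500 to 1000 eligible women per region per year.

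**Assumptions added here.** Two-sided test, beta-distributed ward rates, equal ward sizes.

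**1. Reproduce the stated power.** With c clusters per sub-arm,

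z_beta = sqrt{(c − 1)(p1 − p0)² / [p0(1 − p0)/m + p1(1 − p1)/m + k²(p0² + p1²)]} − 1.96.

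For c = 30 and m = 10 the denominator is 0.009 + 0.016 + 0.16 × 0.05 = 0.033. Then sqrt(29 × 0.01 / 0.033) − 1.96 = 2.964 − 1.96 = 1.004, which is 84.2% power against 84% stated. So m = 10 is the ward size that reproduces the plan's figure.

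**2. Share of zero wards.** A beta distribution with mean p and CV k has a + b = (1 − p)/(k²p) − 1.
- At 10%: a + b = 0.9/0.016 − 1 = 55.25, so a = 5.525 and b = 49.725.
- At 20%: a + b = 0.8/0.032 − 1 = 24, so a = 4.8 and b = 19.2.

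P(0) is the product of (b + i)/(a + b + i) over i = 0 to m − 1. At m = 10 this gives 37.8% in 2a (20.4 of 54 wards) and 15.5% in 2d (8.3 of 54). Without between-ward variation (CV 0) the shares are still 34.9% and 10.7%.

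**3. Likely ward size.** Five regions over 216 wards: 5 × 500 / 216 = 11.6 and 5 × 1000 / 216 = 23.1. The implied mean is about 12 to 23 women, above the minimum of 10.

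**4. Effect if logs are used and zero wards dropped (CV 0.4).** The true ratio is 2.0, a log effect of 0.693.

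| Women per ward | Zero wards, 2a | Zero wards, 2d | Ratio of geometric means | Share of log effect kept |
|---|---|---|---|---|
| 10 | 37.8% | 15.5% | 1.41 | 50% |
| 12 | 31.7% | 11.5% | 1.49 | 57% |
| 17 | 20.9% | 5.8% | 1.65 | 72% |
| 23 | 13.2% | 2.9% | 1.79 | 84% |

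At 10 women the log effect is 0.346, and 0.346 / 0.693 = 0.50. On the percentage-point scale, the mean proportions in the non-zero wards are 16.1% and 23.7%, so the difference falls from 10.0 to about 7.6 points.

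**5. Power at m = 10, 10% vs 20% (8,000 simulated trials).** The t-test on untransformed proportions with all wards gives about 86% with 30 wards per sub-arm and 98% with 54. The t-test on logs without the zero wards gives about 57% and 84%.

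**6. Patching the zeros.** Adding 0.5 before taking logs gives a ratio of about 1.71 at m = 10, so this is only a partial remedy.

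**7. Persistence.** The 37.8% and 15.5% in step 2 are also the wards with no initiators, hence with no persistence proportion. From the same distribution at m = 10, exactly one or two initiators occur in 35.6% + 18.1% = 53.7% of 2a wards. Among 2a wards with any initiator that is 53.7 / 62.2 = 86%.

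**8. Districts.** With 500 to 1000 women and 5% to 15% uptake, the chance of a zero district is at most 0.005%.

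**The case against.** The strongest reply is that the harm needs two steps the plan does not take. The log step is conditional, only a similar approach is extended to the sub-arms, and nowhere are zero wards said to be excluded. The untransformed t-test keeps every ward for uptake. The case for transforming is also weak: ward proportions at 10 women have skewness of about 1.0 (2a) and 0.7 (2d), yet the untransformed t-test with 54 wards per sub-arm had a simulated type I error of 4.9% against a nominal 5%. All of this stands. A reader might infer that following the plan removes zero wards, or that skewness will force the log scale. The documents support neither.

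Ten women is a stated minimum, and the halving applies only to the log scale at that size. This stands too, and it is why the range for 12 to 23 women is given. One could go below 10 by supposing that only the 6 months of champion and mobilization activity count. The plan does not define a separate outcome window for the sub-arms and states at least 10 women per ward, so I place no weight on that.

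Finally, the comparison is exploratory and the primary analysis is untouched. That limits the importance of the point. It does not remove it: the written option cannot be computed on all wards, the handling of zeros is left open, and for persistence even the untransformed t-test loses wards, more of them in 2a.

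**Conclusion.** The concern holds as a gap in the ward-level specification. The log option cannot be applied to all wards: about 38% of 2a wards and 15.5% of 2d wards would have zero initiations at the minimum ward size, and about 13% and 3% at 23 women. Were logs used and zeros dropped, between 50% of the log effect (10 women) and 84% (23 women) would remain. For persistence, wards without initiators drop out whatever the scale, and wards with one or two initiators weigh as much as larger ones.

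Two stronger conclusions should be resisted. The plan does not commit to an analysis that halves the effect; that figure is a conditional worst case at the minimum ward size. Nor is the primary Arm 1 vs Arm 2 comparison at risk, since zero districts are practically impossible.

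The sizes rest on the plan's uptake figures and CV of 0.4, beta-distributed ward rates and equal ward sizes. The need for a rule does not depend on those details. It should be settled before the ward data are analysed.

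**What to change.** In section 7.C:

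- Restrict the log option to the district-level Arm 1 vs Arm 2 comparison.
- For the ward-level sub-arm comparisons, pre-specify an analysis without log transformation that includes the site strata used in randomization.
- For uptake, untransformed ward proportions with site effects are adequate.
- For 1- and 4-month persistence, a grouped-binomial model of counts with site strata and ward-robust or overdispersion-scaled standard errors is preferable, because it weights wards by their initiators. The same model could serve for uptake, where zero wards enter without adjustment.
- State that wards without initiators contribute nothing to persistence, and report their number by sub-arm.

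The cost is a few sentences of SAP text and no new data. The downside is that the ward-level method will differ from the district-level one, which the plan should say openly.
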